16 However, this study did not report outcome related with LCOS. Another study measured inflammatory mediators
17 (IL-6, IL-8, IL-10, and TNF α) and cardiac markers (N-terminal pro-B-type natriuretic peptide and troponin I) in 46
18 cardiac pediatrics patients¹⁴. Multivariate logistic regression identified pre-operative N-terminal pro-B-type natriuretic
19 peptide □ 470 fmol/ml and post-operative IL-8 at 4 hour □ 128 pg/ml were significantly related with LCOS events.

20 The most recent study published in 2021¹⁵ evaluated inflammatory mediators in 31 patients with congenital
21 heart disease. It showed higher preoperative IL-10 and 24-hour postoperative IL-8 level were associated
22 significantly with LCOS.

23 **Research methodology**

24 **9.1. Study design:** prospective diagnostic study

25 **9.2. Setting of the study/Trial site:** 8-bed pediatric intensive care unit, Songklanagarind Hospital, Hat Yai,
26 Songkhla

27 **9.3. Target population:** Children with cardiac disease in Songklanagarind hospital who undergone open
28 cardiac surgery with cardiopulmonary bypass (age < 18 years old)

29 **9.4. Study population**

30 **9.4.1. Inclusion criteria:**

- 31 - Children aged 0-18 years old with either congenital or acquired cardiac disease
- 32 - Undergone cardiopulmonary bypass for cardiac surgery
- 33 - Be admitted in PICU for post-operative care

34 **9.4.2. Exclusion criteria**

- 35 - Preterm infant (GA < 37 weeks) or weight less than 2 kg

1 - Patient who weaned off cardiopulmonary bypass and required extracorporeal membrane
2 oxygenator (ECMO) before leaving the operating room
3 - Patient who required emergency cardiac operation within 24 hour after hospitalization
4 - Patient who had significant residual left side outflow tract obstruction (e.g., coarctation of
5 aorta, interrupted aortic arch) which defined by difference of SBP between upper and lower
6 extremities more than 10 mmHg
7 - Patient who had already participated in another research project
8 - Patient who does not have both arterial line and central line catheter back from operating room
9 - Parents or legal guardian refuse to inform consent.

10 9.4.3. Withdrawal criteria:

11 - Parents or legal guardian request to withdraw from research

12 9.4.4. Termination criteria: none

13 **9.5. Sample size calculation**

14 For the 1st objective, we apply diagnostic study as follows:

$$n = n_0 / \text{prevalence or incidence of disease}$$

$$n_0 = \frac{(Z_{\alpha/2})^2 P (1-P)}{d^2}$$

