15	Where: Sensitivity (p)	= 0.85
16	Precision (d); not more than 10% of p	= 0.09
17	Alpha	= 0.05

18 We applied the sensitivity of lactate > 3 mmol/L for major morbidity, which defined as at least one of
19 complications (i.e., neurological, pulmonary, gastroenteric, and need for extracorporeal membranes oxygenation or
20 ventricular-assist device, or sepsis)¹⁶.

21 Estimated patient (n_0) is 61 cases. Based on 48% of incidence of LCOS-related outcome last year in our
22 study setting, the required total sample size including non-disease and disease participants will be 128 (=61/0.48).

23 Regarding with our sample size calculation for two objectives and an estimate of 20% of unusable data
24 from a sample of 128 participants has been considered. The final sample size is 154 participants for sensitivity of
25 0.85. However, we will collect blood sample for inflammatory markers in 32 patients for preliminary analysis.

26 **9.6. Variables of the study**

27 9.6.1. Dependent variable: poor outcomes indirectly represented from low cardio output syndrome

28 - LCOS-related poor outcome is modified from the study of Drennan SE, et al and Carmona, et al^{14, 15}
29 which consisting of at least two of the following criteria within 48 hour post operatively:

- 1 a. Clinical findings suggestive of LCOS: prolonged capillary refill > 3 s, systolic blood pressure < 5th
2 percentile for age and gender, persistently elevate of LA pressure above 10 mmHg for at least 6 hr
3 , low urine output (< 1mL/kg/hr) for at least 6 hour despite diuretic use
- 4 b. Laboratory findings suggestive of LCOS: persistently elevated lactate (>2 mmol/L), metabolic
5 acidosis with an increase in the base deficit (>4 mmol/L) for at least 6 hr consecutively.
- 6 c. Vasoactive-inotropic score (VIS) \square 20
- 7 d. Any unplanned surgical reinterventions, cardiac arrest, or utilization of extracorporeal membrane
8 oxygenator (ECMO) within 48 hours
- 9 e. Left ventricular fraction less than 50% by echocardiography

10 The LCOS-related outcome will include both anatomical LCOS and physiological LCOS that caused by

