3. Preoperative blood sample 1.5 mL will be collected for inflammatory markers level at the same time when patient has intravenous access preparing for NPO or other preoperative blood sample.

4. Patient goes on open heart cardiac surgery and will be admitted directly to pediatric intensive care unit (PICU) for postoperative care.

5. Blood sample for blood gas 0.3 mL for each central line catheter and arterial line catheter and inflammatory markers 1.5 mL drawn from arterial line will be collected at 0, 6, 12, and 24 hours after PICU arrival. Arterial and venous blood gas are accepted if samples are collected within 5 minutes of each other. We allow time gap for collecting blood +/- 1 hr from schedule due to unpredictable ICU occupy.

6. Attending physician provides standard care for post cardiac operation. The decision of treatment by attending physician will not be involved by researchers. Inflammatory markers results will be reported after patient is discharged from hospital to minimize influence of result to physician's decision on treatment.

1 7. Cardiologist will perform echocardiography to evaluate left ventricular function and anatomical defect
 2 that could mimic signs of LCOS within 48 hours postoperatively.

3 8. Researcher prospectively collects postoperative variables including hemodynamic variables and
 4 therapeutic interventions and patient's outcome.

5 9. The primary study endpoint is poor outcome related to LCOS. The secondary endpoints are 28-day
 6 ventilator free day, ICU free day, deaths and correlation of AVCO₂ with other cardiac output surrogates
 7 (AVO₂, ScvO₂ and arterial blood lactate).

8 10. If either central line or arterial line catheter are displaced before 24-hour, remaining data will be
 9 recorded as missing data.

10 **Describe procedures/process of the study. Show how research methodology in the study is different from
 11 the routine practice?**

Processes which are routine practice	Processes which are research
1. Pre-operative lab sampling; CBC, Coagulogram, electrolyte, group match for blood component	1. Adding inflammatory markers to pre-operative lab
2. Serial ABG sampling q 2-6 hr depend on severity of patient	2. Extra 2 blood sampling for VBG (0.3 mL each)
3. Serial VBG sampling q 24 hr	3. Mandatory blood sampling q 6 hr x 5 times for inflammatory markers (1.5 mL each)

12 **9.8. Study instrument(s) and outcome measurement(s)**

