- Blood sample for blood gas analysis 0.3 mL will be drawn from arterial line and central venous catheter each with different time less than 5 minutes. The arterial and venous gas will be analyzed by ABL800 Basic (Radiometer, Copenhagen, Denmark) which is located in PICU
- Blood sample for inflammatory markers 1.5 mL will be collected into 3 mL vacutainers without anticoagulant. Collected blood will be kept on room temperature and sent to division of immunology and virology within 3 hours after collecting. Samples will be centrifuged at 500 x g for 15 minutes at 4°C. Supernatant will be transferred to a clean polypropylene tube. Separated serum will be aliquoted into cryogenic vial and stored at -80°C until analysis.
- Serum cytokines (TNFα, IL-1β, IL-6, IL-8, IL-10) will be quantified in serum using multiplex immunoassays (Bio-Plex Pro Human Screening Panel 5plex XPLEX, Bio-Rad, California, USA). The plate will be read on Bio-Plex®200 array reader (Bio-Rad, California, USA) and analyzed using Bio-Plex Manager™ software. Sample will be run in duplicates and cytokine level will be quantified via comparison to standard curve.

1 **9.9. Data collection methodology**

2 - Data record form consists of 5 parts: patient's profile, characteristic of cardiac disease, intra- and post-
3 operative intervention, laboratory values at 4 different time points, and PICU outcome. Researcher will
4 collect data via electronic medical records, nursing record form, and blood gas record sheet of each
5 participant.

6 **9.10. Data management**

7 - All of data will be collected in record form before putting in Epidata program. Study codes will be used on data
8 collection and data document instead of hospital number of patients.

9 **9.11. Statistical analysis**

10 Descriptive part:

11 - For continuous data (i.e., AVCO₂, ScvO₂, lactate, inflammatory markers, and others), we will use mean
12 (\pm SD) in normal distribution and median (\pm IQR) in non-normal distribution. We will use percentages for
13 categorical data (i.e., LCOS-related poor outcome).

14 Analytic part:

15 - Two means of the continuous outcomes will be compared using t-test or Mann Whitney U test. Two or
16 more proportions of the categorical outcomes will be compared using Chi-square or Fisher-exact test.
17 - We will apply the pairwise correlation analysis among independent variables: AVCO₂, lactate, ScvO₂,
18 inflammatory markers with time lagged factor.

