14 predict LCOS in children who undergone CPB, this new bedside surrogate (AVCO₂) might be another
15 bedside tool to detect post-operative LCOS earlier in order to improve outcome.

16 **10.4. Informed consent process: Process/method of invitation the participants to participate in the
17 research, such as personal contact, referral from other(s), brochure, and announcement, etc.**

18 - Researcher will introduce research project verbally to cardiac pediatrics patient or their legal
19 guardians at cardiac outpatient clinic when he/she are scheduled to have cardiopulmonary bypass
20 surgery at Songklanagarind Hospital and give consent form to legal guardians to sign. Researcher
21 will later request collect the inform consent when he/ she is admitted in hospital 24 hours in
22 advance.

23 - If patient has already been admitted in hospital for any reason and have schedule for surgery,
24 researcher will inform patient or legal guardians 48 hours in advance.

25 **10.5. Procedure specifying for research participant withdrawal from the study**

26 - Blood sample taking will be ceases immediately after participant/legal guardians withdrawn from
27 the study

28 - Data collected from a withdrawn patient will be used in the study analysis. Data after patient
29 withdraw will be inserted as missing data.

30 **10.6. Clearly indicate person(s) responsible for payment for treatment of complications and adverse
31 effects**

32 There is no any intervention or therapeutic trial in this study.

33 **10.7. Compensation for research participant**

34 Yes, please provide detail:.....

1 ✓ No, please provide reasons: patient does not have to spend extra time or any effort during the
 2 research, so there is no compensation will be provided in this study

3 **10.8. Does the study involve biological specimen collection? If yes, also explain how the investigator
 4 manages the leftover specimen.**

5 The study will collect additional total 8.1 mL of blood for inflammatory mediators (1.5 mL each x 5
 6 times for inflammatory markers and extra blood sampling 0.3 mL x 2 times for VBG analysis during
 7 study period). After complete analysis, leftover specimen will be discarded immediately.

8 **10.9. Research project with special ethical consideration (if applicable)**

9 **11. Limitation(s) and barrier(s) of the study (if applicable) and plans for mitigation**

10 - The time of blood sampling might be inaccurate as schedule. The protocol allows the time gap 1 hour from

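### Section 10.5 has one level of withdrawal and sets all later data to missing, so stopping the research blood draws also ends collection of outcomes that mostly come from care records

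*Combined protocol and SAP*

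**What the plan says.** - **Route.** Section 9.4.3 gives a single withdrawal criterion: "Parents or legal guardian request to withdraw from research". There is no option to leave only part of the study.
- **Consequence.** Section 10.5 has three parts. On sampling: "Blood sample taking will be ceases immediately after participant/legal guardians withdrawn from" the study. On data already held: "Data collected from a withdrawn patient will be used in the study analysis". On data after that point: "withdraw will be inserted as missing data". No exception is made for outcomes.
- **Research procedures.** The routine-versus-research table in 9.7 lists only blood sampling as research. Beyond the pre-operative cytokine sample, the entries are "Mandatory blood sampling q 6 hr x 5 times for inflammatory markers (1.5 mL each") and "Extra 2 blood sampling for VBG (0.3 mL each").
- **Source of outcomes.** Under 9.9 the researcher will "collect data via electronic medical records, nursing record form, and blood gas record sheet of each" participant. Step 6 of 9.7 leaves treatment to the attending physician as standard care.
- **Primary outcome.** LCOS-related poor outcome (9.6.1) is a composite "which consisting of at least two of the following criteria within 48 hour post operatively". Criterion e is left ventricular function on echocardiography, which 9.7 makes a study step (step 7) and the table places in neither column.
- **28-day outcomes.** Ventilator-free and ICU-free days run to day 28 and are zero for children who die (9.6.1).
- **Analysis.** Section 9.11 has no rule for missing outcomes.

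**The concern.** Blood drawing is the only burden the protocol names: the risks in 10.1 are infection and anaemia from sampling, and 10.7 says participation takes no extra time or effort. A wish to stop the draws is therefore a foreseeable reason to withdraw. It would normally arise while sampling is under way, and the last scheduled sample is at 24 h, so such a withdrawal comes before the 48 h outcome window closes.

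Take a child withdrawn at hour 8. The 0 h and 6 h AVCO₂ values are kept. Unless two criteria have already been met, the 48 h outcome is unknown, and those values cannot contribute to sensitivity, specificity, predictive values or the ROC curve in 9.11. Most of the missing outcome information would still exist in the child's records.

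The loss can also be selective. A case can be settled early, but a non-case is settled only at 48 h. With no rule in 9.11, the handling of unclassified children would be chosen after the data are seen.

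**Working it through.** **1. Who keeps a usable outcome under 10.5 (read with 9.6.1)**

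- Withdrawn before 48 h, two criteria already met: remains a case.
- Withdrawn before 48 h, fewer than two criteria met: cannot be classified.
- Withdrawn after 48 h: primary outcome intact.
- Withdrawn before day 28, alive at that time: ventilator-free and ICU-free days lost. Only a death already recorded fixes them (at zero).
- Withdrawn before PICU arrival: no postoperative marker value, so nothing to analyse for accuracy in any case.

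**2. The plan's sample size (9.5)**

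Inputs: sensitivity p = 0.85, precision d = 0.09, two-sided alpha 0.05 (z = 1.96), incidence 48%, unusable data 20%.

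- n₀ = z²p(1 − p)/d² = 60.47, rounded up to 61 cases.
- 61/0.48 = 127.08, rounded up to 128 children.
- 128 × 1.20 = 153.6, rounded up to 154. The plan's figure reproduces.
- The allowance is 154 − 128 = 26 children for all causes; the share for withdrawal is not stated.

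**3. Precision if withdrawal loses outcomes**

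The documents give no withdrawal rate, so w (the share of children whose outcome is lost) is an assumption. Cases and non-cases are taken to be lost in proportion.

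Half-width = 1.96 × √[0.85 × 0.15 / (154 × (1 − w) × 0.48)]

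| w (assumed) | Children lost | Cases left | Half-width |
|---|---|---|---|
| 0 | 0 | 73.9 | 0.081 |
| 2% | 3.1 | 72.4 | 0.082 |
| 5% | 7.7 | 70.2 | 0.084 |
| 10% | 15.4 | 66.5 | 0.086 |

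All are inside the planned 0.09 when withdrawal is the only loss.

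**4. Selective loss: observed incidence**

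Here w is the share withdrawn before 48 h, withdrawal is unrelated to the eventual outcome, and f is the fraction of withdrawn eventual cases who had already met two criteria. Unclassified children are left out.

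Observed incidence = [0.48(1 − w) + 0.48wf] / {[0.48(1 − w) + 0.48wf] + 0.52(1 − w)}

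- f = 0: 48.0% at any w.
- f = 1 (the maximum), w = 2%: 0.48/(0.48 + 0.5096) = 48.5%.
- f = 1, w = 5%: 0.48/(0.48 + 0.494) = 49.3%.

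**5. Sensitivity at the extremes**

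Losing non-cases cannot change sensitivity. Losing cases changes it only if their marker results differ from those of the cases retained. With a true sensitivity of 0.85 and 5% of cases lost, the observed value is (0.85 − 0.05)/0.95 = 0.842 if every lost case was marker-positive, and 0.85/0.95 = 0.895 if every one was marker-negative. At 2% the range is 0.847 to 0.867. These are outer limits, not expectations.

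**The case against.** The strongest defence is that 10.5 does what a withdrawal from research should do: it keeps what was collected with permission and collects nothing more. For a parent who wants out altogether, that is right, and the fix below keeps it. What stands against 10.5 is only that it offers no lesser step.

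Further points for the plan are sound and limit the finding:

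- **A reader might infer that every outcome comes from routine records and is lost needlessly.** The documents do not support that. The echocardiogram is a study step that feeds criterion e and is not listed as routine. Continued reading of records also needs the parent's agreement. The accurate statement is that most components come from care records.
- **A reader might infer that withdrawn children will be counted as free of LCOS.** Section 10.5 makes later data missing, not negative. The remaining gap is that 9.11 does not say what happens to a child whose outcome is missing.
- **A reader might infer a heavy burden, and more withdrawals among small or sick children.** Section 9.5 plans cytokine sampling in only 32 patients. The other 154 − 32 = 122 would have two extra venous gases of 0.3 mL, 0.6 mL in all, and 10.1 limits the volume drawn by body weight. Nothing in the documents links withdrawal to size or severity.
- **The consent pages were not available.** They may already offer a partial withdrawal. The text of 10.5 does not.

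**Conclusion.** The point holds in a limited form. The protocol does not separate stopping research blood draws from ending outcome collection, and the consequence depends on timing: the primary outcome is at risk only for withdrawal before 48 h, and the 28-day outcomes only for withdrawal before day 28.

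The size is unknown, because no withdrawal rate is given, and probably small. At an assumed 2–5% loss the effect on precision is slight. The shift in incidence is at most about one percentage point, provided withdrawal is unrelated to the eventual outcome. The 20% allowance can absorb a precision loss of this size, but it does nothing about selective loss.

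A reader might go further and conclude that the primary accuracy result is biased. The documents do not show that: it would need lost cases to differ in marker results from retained ones, and there is no evidence either way. This is an inexpensive improvement to make, not an error that undermines the design.

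**What to change.** Reword 10.5, and align the consent form if it does not already say this, to offer two levels:

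- **(a) Stop research blood sampling only.** If the parent agrees, outcomes from care records, and the study echocardiogram, are still collected to 48 h, day 28 and hospital discharge.
- **(b) Full withdrawal.** No further data are collected; data already held are kept, as now.

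Add to 9.11: for full withdrawal before 48 h, report the number and timing of children who cannot be classified, and give the primary accuracy measures with those children set first to all cases and then to all non-cases.

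The cost is a minor ethics amendment, one extra question at withdrawal and slightly more chart review. No procedure is added.
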